4.3 Inclusion Criteria

The following are requirements for entry into the study:

General Inclusion Criteria

1. Male or female patients, 50 years of age or older at the time of informed consent
2. Patient has completed/signed an informed consent prior to conduct of any study-related procedures or examinations, is able to follow study instructions, and is likely to complete all required visits
3. Patient has provided, at screening, written documentation in accordance with the relevant country and local privacy requirements (eg, Written Authorization for Use and Release of Health and Research Study Information and written Data Protection consent, as required by regional health authorities)

Ocular Inclusion Criteria (Study Eye)

[Redacted text block]

[Redacted text block]

6. BCVA \leq 73 and \geq 24 letters (20/40 to 20/320 Snellen equivalents, respectively) at screening and at baseline (day 1, prior to treatment) visits

[Redacted text block]

Ocular Inclusion Criteria (Non-study Eye)

8. BCVA of 34 letters (Snellen equivalent 20/200) or better at baseline (day 1), prior to treatment

[figure not shown]
Approval Date: 10-Apr-2018

[figure not shown]

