4.2 Baseline Characteristics

Baseline characteristics include height (cm), weight (kg), iris color, lesion type (predominantly classic, minimally classic, or occult), lesion size, subretinal or intraretinal fluid, intraretinal cysts, pigment epithelial detachments, polypoidal choroidal vasculopathy, and smoking status. Ocular characteristics of the study eye at baseline include lens status, study eye as the better-seeing eye (defined as baseline $BCVA_{study-eye} > BCVA_{non-study eye}$), BCVA, CRT, and intraocular pressure. Summaries of baseline characteristics will be done for the ITT and PP populations.

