5.1 Collection of Primary Efficacy Measurement and Derivation of Primary Efficacy Variable

BCVA will be recorded on the CRF as the number of letters correctly read. For a given eye, the 4-meter distance (standard) of BCVA is tested first. If the patient correctly reads at least 20 letters at 4 meters, BCVA score will be set as the sum of 30 and the number of letters read correctly. If the patient correctly reads less than 20 letters at 4 meters, the BCVA is measured again at 1 meter. The BCVA score will be set to the number of letters read correctly at 1 meter plus the number of letters read correctly at 4 meters. For each patient, BCVA data will be collected for both eyes at the screening, baseline visit (Day 1 but prior to the study treatment), and at Weeks 12, 24, 36, 52, 76, and 104/early exit visits; and for the study eye only at all other scheduled visits.

For patients who received any non-study anti-vascular endothelial growth factor (VEGF) treatments in the study eye, data after the 1st such treatment will be excluded from all efficacy analyses.

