5.3.4 NEI-VFQ-25 Mean Change from Baseline in Composite Score

The NEI-VFQ-25 will be administered at the Baseline/Day 1, and at Weeks 12, 24, 36, 52, 76, and 104/early exit visits. Detailed analyses and analysis visit windows are described in Section 7 for health outcome data analysis.

As a secondary efficacy variable, change from baseline at Week 52 in the overall composite score will be analyzed for superiority testing using the ITT population and MMRM as described in Section 5.3.1 for the key secondary efficacy variable of BCVA change. The model will include the treatment group, region, baseline BCVA in the study eye, baseline VFQ score, visit, and treatment-by-visit interaction as fixed covariates using an unstructured covariance matrix. Treatment differences and the corresponding 95.1% confidence intervals will be constructed using the MMRM model.

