No interim analyses are planned for this study. However, an independent DSMC will assess the unmasked safety data during the study. To preserve an overall alpha of 0.05 for the study, an adjustment of 0.001 will be made and an alpha level of 0.049 will be used for testing purposes. Therefore, 95.1% confidence intervals will be constructed for the primary efficacy analysis.

Statistical Analysis Plan for 150998-005 CSR (Amendment 2)

11. Deviations from Protocol

There are no deviations from the current study protocol.

12. References

Yan X. and Su X.G Stratified Wilson and Newcombe confidence intervals for multiple binomial proportions. Statistics in Biopharmaceutical Research. 2010;2(3):329-335.

13. Amendment(s)

13.1 Amendment 1

The following changes were made in Amendment 1:

13.2 Amendment 2

The following changes are made in Amendment 2:

- For Japan Pharmaceuticals and Medical Devices Agency (PMDA) review, clarified the gatekeeping procedure for multiplicity adjustment to be applied to statistical tests of secondary efficacy variables (Section 10)

14. Appendix A

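### The NEI-VFQ-25 model has no fellow-eye term although both eyes are measured at baseline; adding one may give this superiority test slightly more precision

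*SAP*

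**What the plan says.** The NEI-VFQ-25 composite is one of the secondary endpoints. SAP 5.3.4 states the comparison: "change from baseline at Week 52 in the overall composite score will be analyzed for superiority testing using the ITT population". The covariates are then listed: "The model will include the treatment group, region, baseline BCVA in the study eye, baseline VFQ score, visit, and treatment-by-visit interaction". The output is a set of contrasts with intervals: "Treatment differences and the corresponding 95.1% confidence intervals will be constructed using the MMRM model". The same subsection sends the reader to SAP Section 7 for detailed health-outcome analyses; that section is not in the public text.

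Two other places show what is available at baseline:

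- SAP 5.1: "BCVA data will be collected for both eyes at the screening, baseline visit".
- SAP 4.2 lists "study eye as the better-seeing eye" among the ocular baseline characteristics, defined by comparing baseline BCVA between the two eyes. It is used there for summary only.

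Randomization (SAP 1.1) is by region and stratified on BCVA, CRT and lesion type, all in the study eye. Protocol 7.3.2 says only that the questionnaire is handled much as BCVA change is. The supplied SAP is labeled 150998-005 and the protocol 150998-006, so the point concerns the SAP text as supplied.

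**The concern.** The other secondary endpoints are study-eye measurements, for which study-eye covariates are the natural choice. The questionnaire is answered by the person, who sees with both eyes. SAP 5.3.4 does adapt the model to this outcome: compared with SAP 5.3.1 it drops the CRT, lesion-type and visit-by-BCVA terms and adds the baseline VFQ score. The acuity covariate is still for one eye.

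Entry criteria allow the study eye to be either the better or the worse one. Protocol 4.3 admits study eyes from 24 to 73 letters and requires of the other eye "BCVA of 34 letters (Snellen equivalent 20/200) or better at baseline (day 1), prior to treatment", with no upper limit shown. If treating the better eye moves the composite more than treating the worse eye, eye status predicts change. Two patients with the same baseline score may then differ in expected change because different eyes limit them. Neither the stratification nor the model uses that information.

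What is at stake is the width of an interval in a superiority test. The SAP's amendment list also mentions gatekeeping of secondary endpoints for the Japanese regulator, so the endpoint may have a formal role there. The section it cites is not visible.

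**Working it through.** **The plan's own figures.** The documents give no SD, effect size or power for the questionnaire. The only sample-size statement is for stable vision (SAP 1.2), and it reproduces:

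- n per group = (1.960 + 1.645)² × 2 × 0.9 × 0.1 / 0.10² = 234, against 240 stated.
- Power at 240: 0.10 / √(0.18/240) = 3.652. Subtracting 1.960 gives 95.5% at alpha 0.05; subtracting 1.969 gives 95.4% at alpha 0.049.
- 240 / (1 − 0.20) = 300 per group, or 900 in all.
- Alpha: 0.05 − 10 × 0.0001 = 0.049, as SAP Section 9 has it: "an adjustment of 0.001 will be made and an alpha level of 0.049 will be used for testing purposes".

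Nothing in the present point changes these figures.

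**Effect of an added baseline covariate.** Let r be the partial correlation of the added terms with Week 52 VFQ change, given the covariates already in the model. Residual variance is multiplied by 1 − r². From an illustrative starting power of 80%,

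new power = Φ((1.969 + 0.842) / √(1 − r²) − 1.969).

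| Assumed r | Variance reduction | SE reduction | Equivalent increase in patients | Power from 80% |
|---|---|---|---|---|
| 0 | 0% | 0% | 0% | 80.0% |
| 0.1 | 1% | 0.5% | 1% | 80.4% |
| 0.2 | 4% | 2.0% | 4% | 81.6% |
| 0.3 | 9% | 4.6% | 10% | 83.6% |

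At r = 0.3, a starting power of 50% becomes 53.8%, and 90% becomes 92.5%. The formula treats Week 52 as a single measurement. In the MMRM a plain fixed covariate delivers this gain in full only if its association with change is about the same at each visit.

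**Where in the range.** An illustrative simulation used these assumptions, none of them from the documents:

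- standardized study-eye acuity S, and fellow-eye acuity equal to 0.2 S plus unit noise;
- true function equal to 0.2 S plus 0.3 or 0.5 times fellow-eye acuity, plus noise of SD 0.7;
- VFQ measured with error of SD 0.4 at each time;
- extra change of 0, 0.3 or 0.6 (scaled by 0.8) when the study eye is the better one.

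Residual variance with both new terms, relative to the model with study-eye acuity and baseline VFQ only:

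| Fellow-eye weight | Shift 0 | Shift 0.3 | Shift 0.6 |
|---|---|---|---|
| 0.3 | 0.9951 | 0.9949 | 0.9722 |
| 0.5 | 0.9881 | 0.9919 | 0.9769 |

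The reduction is 0.5% to 2.8%, a joint partial r of about 0.07 to 0.17. By the formula above, 2.811/√0.995 − 1.969 = 0.849 gives 80.2%, and 2.811/√0.972 − 1.969 = 0.882 gives 81.1%. That is +0.2 to +1.1 points.

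**The case against.** The strongest reply is that nothing here is wrong. Leaving a prognostic covariate out of a randomized linear comparison neither biases the contrast nor inflates type I error. The model already holds the outcome's own baseline, which carries whole-person visual function. The better-eye indicator is built from study-eye BCVA, also in the model, so part of it is accounted for. All of this stands, and it is why the gain is probably small.

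Three stronger readings are tempting and are not supported:

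- *Precision is lost.* That would need a non-zero partial correlation after adjustment for baseline VFQ. The documents give none, and they do not say how the composite depends on the better or worse eye.
- *The gain can be read off as p(1 − p)(D/s)²*, where p is the share of better-eye patients and D/s their difference in change in residual SDs. With p from 0.2 to 0.4 and D/s from 0.2 to 0.6 this gives 0.6% to 8.6%. But it uses the indicator's unconditional variance, while only the part not explained by the existing covariates counts, and p and D/s are themselves guesses.
- *Chance imbalance distorts the result.* Take 300 per arm, an assumed 30% better-eye share and an assumed 0.4 SD difference. A one-SD imbalance is √(2 × 0.3 × 0.7/300) = 3.7 percentage points, which moves the contrast by 0.015 SD. The standard error is √(2/300) = 0.082 SD, so the shift is about 18% of it. The planned interval already allows for this, and the existing covariates remove some of it.

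The 80% starting power is also hypothetical. If the arms are equal on the questionnaire, better precision narrows the interval but adds no power for superiority. Finally, Section 7 might use fellow-eye information. Even so, SAP 5.3.4 states explicitly the model for this secondary endpoint. None of these points shows that adding the terms would do harm.

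**Conclusion.** The point holds as an optional efficiency improvement, not as an error. The stated model makes no use of fellow-eye acuity or better-seeing-eye status, both available before treatment. The likely benefit lies toward the bottom of the 0 to 9% variance range. That judgment rests on an assumed partial correlation of at most 0.3, on illustrative simulation coefficients, and on a hypothetical 80% starting power. The clinical premise that eye status predicts change in the composite is also an assumption. No figure in the plan and no primary or key secondary conclusion is affected.

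**What to change.** In the SAP 5.3.4 MMRM, add two fixed covariates: baseline BCVA in the non-study eye, and the better-seeing-eye indicator as SAP 4.2 defines it. Keep every other term, the covariance structure and the ITT population as they are. Confirm that Section 7 states the same model.

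The change should be made before the study is unmasked to the restricted group at the Week 52 database lock (SAP 1.3); afterwards it would be post hoc.

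The cost is one sentence of SAP text and about two degrees of freedom among roughly 900 patients. No new data are needed. SAP 2.4 already lets a screening value stand in for a missing baseline one, so few if any patients should drop out of the model for want of a fellow-eye reading.

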6.1 Study Treatment – Exposure and Administration

6.1.1 Exposure to Study Treatments

Exposure to study treatment will be evaluated by the number of study injections (including sham), the number of active study injections (excluding sham) and exposure days. Patients who have missed any study treatment(s) will be enumerated. Duration of treatment based on the days from the 1st to the last active study injections (excluding sham) will be calculated. Descriptive statistics will be tabulated for each treatment group using the safety population.

6.2 Adverse Events

A TEAE is an adverse event that occurs after the initiation of the study treatment (ie, the onset date is the same as or after the study treatment date), or an adverse event with onset prior to the study treatment that worsened in severity or became serious after the initiation of the study treatment. The incidence of TEAEs will be calculated by treatment group and presented as the number and percentage of patients experiencing the TEAE during the reporting period.

The following summaries of TEAE data will be performed: 1) overall summary, 2) all TEAEs regardless of causality, 3) treatment-related TEAEs, 4) ocular TEAEs (study eye versus non-study eye), 5) nonocular TEAEs, 6) treatment-related ocular TEAEs, and 7) TEAEs of special interest. An additional summary will be provided for 8) treatment-emergent serious adverse events (TE SAEs) and 9) AEs leading to study discontinuation.

The 1) overall summary will present the number and percentage of patients with TEAEs, ocular/nonocular TEAEs in the study eye, treatment-related ocular/nonocular TEAEs, AEs leading to study discontinuation, TE SAEs, and death in each treatment group. Treatment-related ocular TEAEs will also be summarized for injection-related and drug-related TEAEs. Injection-related TEAEs are those TEAEs marked as related to the study treatment administration.

Further, tabulations of TEAEs or TE SAEs based on MedDRA coded terms, primary system organ class (SOC) and/or preferred terms (PTs) will be sorted by the frequency of occurrence as detailed below.

- Summary for 3) treatment-related TEAEs, 5) nonocular TEAEs, 8) TE SAEs, and 9) AEs leading to study discontinuation will be sorted by primary SOC in alphabetical order. Within each SOC name, TEAEs (TE SAEs or AEs) will be tabulated by PT in descending order. A patient with multiple occurrences of the same PT within the reporting period will be counted only once for that PT.
- Summary for 2) TEAEs by severity will be sorted by primary SOC in alphabetical order and by the worst severity (maximum severity) experienced for a given patient. Within each SOC, TEAEs will be tabulated by PT in descending order and by severity. The severity of a TEAE is defined as the greater of the onset severity and maximum severity recorded on the CRF for each unique PT reported by the patient.

• Summary for 4) ocular TEAEs, 6) treatment-related ocular TEAEs, and 7) TEAEs of special interest of intraocular inflammation will be sorted by preferred term in descending order. A patient with multiple occurrences of the same preferred term within the reporting period will be counted only once for that PT.

All tabulations will be sorted in descending order of frequency following this sequence from left to right: starting from abicipar groups 2Q8, 2Q12, and ranibizumab every 4 weeks (rQ4).

For the Week 52 analysis, AEs reported from baseline to Week 52 will be determined by AE onset date using the following criteria:

- For patients who completed the Week 52 visit, include AEs with an onset date ≤ Week 52 visit date
- For patients who did not complete the Week 52 visit due to early dropout or missed visit, include AEs with an onset date ≤ 365 days from the date of the 1st injection prior to early exit

For cases where the AE onset date is partially or completely missing and does not allow for a full determination of whether the AE occurred within the Week 52 period, those AEs will be included in the Week 52 analysis.

6.2.1 TEAEs of Special Interest

TEAEs of special interest include intraocular inflammation and those potentially related to systemic VEGF inhibition. TEAEs related to systemic VEGF inhibition will be categorized as arterial-thromboembolic events (ATEs, defined as nonfatal stroke, nonfatal myocardial infarction, or vascular death [including deaths of unknown cause]), hypertension, nonocular hemorrhage, proteinuria, and others. Data for these two types of TEAEs will be summarized by MedDRA preferred terms.

TEAEs included in the intraocular inflammation table will follow a two-step selection process: first to identify the MedDRA preferred terms that may represent an intraocular inflammation followed by a thorough medical review of any relevant details reported for the adverse event including ocular examination findings. The incidence of TEAEs for intraocular inflammation of special interest will be summarized by treatment group and presented as the number and percentage of patients. TEAEs identified based on MedDRA preferred terms but not considered as intraocular inflammation of special interest will be displayed in a separate data listing. TEAEs included in the events potentially related to systemic VEGF inhibition table will be identified following the same process. A summary for arterial thromboembolic events or other adverse events that are potentially related to systemic VEGF inhibition will be done by the following categories of ATE, hypertension, nonocular hemorrhage, proteinuria, and others by preferred terms.

In addition, TEAEs potentially related to systemic VEGF inhibition will be summarized separately for patients who received the following anti-VEGF injections in the non-study eye: ranibizumab, bevacizumab, pegaptanib, and aflibercept.

The selection and review of all TEAEs of special interest will be performed in a masked fashion and finalized prior to database lock and study unmasking.

_	
-	

		_	

8. Subgroup Analyses

Subgroup analyses will be performed on the pooled data from the 2 pivotal Phase 3 studies. Analysis will be carried out for the integrated summaries of safety and efficacy. Subgroup analyses will not be performed for the individual clinical studies.

9. Interim Analyses

No interim analyses are planned for this study. However, an independent DSMC will assess the unmasked safety data during the study. To preserve an overall alpha of 0.05 for the study, an adjustment of 0.001 will be made and an alpha level of 0.049 will be used for testing purposes. Therefore, 95.1% confidence intervals will be constructed for the primary efficacy analysis.

Statistical Analysis Plan for 150998-005 CSR (Amendment 2)

11. Deviations from Protocol

There are no deviations from the current study protocol.

12. References

Yan X. and Su X.G Stratified Wilson and Newcombe confidence intervals for multiple binomial proportions. Statistics in Biopharmaceutical Research. 2010;2(3):329-335.

13. Amendment(s)

13.1 Amendment 1

The following changes were made in Amendment 1:

13.2 Amendment 2

The following changes are made in Amendment 2:

- For Japan Pharmaceuticals and Medical Devices Agency (PMDA) review, clarified the gatekeeping procedure for multiplicity adjustment to be applied to statistical tests of secondary efficacy variables (Section 10)

14. Appendix A

Appendix A: Modified Wald Confidence Interval with Stratifications

Single Imputation (LOCF)

Let i=1, 2, ..., k index strata and let p_{1i} and p_{2i} denote stratum-specific response rates for treatment 1 and 2 in stratum *i*, respectively. Let $d_i = p_{1i} - p_{2i}$, where $p_{1i} = \frac{x_{1i}}{n_{1i}}$, with x_{1i} being the number of responders and n_{1i} being the sample size for treatment 1 in stratum *i*. Similar definition for $p_{2i} = \frac{x_{2i}}{n_{2i}}$.

Let
$$p_{1i}^* = \frac{x_{1i}+2}{n_{1i}+4}$$
 and $p_{2i}^* = \frac{x_{2i}+2}{n_{2i}+4}$

With corresponding variance,

$$v_{1i} = \frac{p_{1i}^*(1-p_{1i}^*)}{n_{1i}}$$
 and $v_{2i} = \frac{p_{2i}^*(1-p_{2i}^*)}{n_{2i}}$

And the variance for the difference in response rates between treatment groups in stratum *i*,

$$v_i = v_{1i} + v_{2i}$$

Define weight $w_i = \frac{n_{1i} * n_{2i}}{n_{1i} + n_{2i}}$

The weighted difference,

$$d = \frac{\sum_{i=1}^{k} w_i d_i}{\sum_{i=1}^{k} w_i}$$

And the variance for the weighted difference is,

$$v(d) = \frac{\sum_{i=1}^{k} w_i^2 v_i}{\left(\sum_{i=1}^{k} w_i\right)^2}$$

The Wald confidence interval for the weighted difference is,

$$d\pm Z_{1-\alpha/2}*\sqrt{\upsilon(d)}$$

where $Z_{1-\alpha/2}$ is the critical value corresponding to the 1- $\alpha/2$ quantile of the standard normal distribution.

Multiple Imputation

Let $V_{(j)}$ denote the variance V(d) for the point estimate from the j^{th} imputed dataset.

Hence, the within-imputation variance over all imputed data can be calculated as following:

$$\bar{V} = \frac{1}{m} \sum_{j=1}^{m} V_{(j)}$$

And the between-imputation variance is $B = \frac{1}{m} \sum_{j=1}^{m} (d_{(j)} - \bar{d})^2$

Where $d_{(j)}$ is the weighted difference for the j^{th} imputation invocation and \bar{d} is the average of weighted differences over all imputation invocations.

The total variance is the combination of within- and between-imputation variance:

$$T = \bar{V} + \left(1 + \frac{1}{m}\right)B$$

For SAS application, plugging in *d* as the MODELEFFECTS and $\sqrt{V(d)}$ as the STDERR for PROC MIANALYZE.

The lower bound of the confidence interval is,

$$LB = \bar{d} - Z_{1-\alpha/2} * \sqrt{T}$$

and the upper bound of the confidence interval is,

$$UB = \bar{d} + Z_{1-\alpha/2} * \sqrt{T}$$

where T is the total variance from imputed data.

IOP is not assessed at 5-min postinjection; only 20 min postinjection

ALLERGAN

Statistical Analysis Plan for AMD P3 CEDAR Amendment 2

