5.2.2 Primary Analyses of Primary Efficacy Variable

The primary analysis of the primary efficacy variable will be performed using the PP population based on a stratified method with Cochran-Mantel-Haenszel (CMH) weights. Within the framework of this method, the difference in the proportions between each abicipar arm and ranibizumab (abicipar group minus ranibizumab group) and the corresponding 2-sided 95.1% confidence interval for non-inferiority testing will be calculated. Specifically, the confidence intervals for treatment group differences will be calculated using the CMH weighted method with the baseline BCVA (\leq 55 versus > 55 ETDRS letters) as a stratification factor as described in Yan and Su (2010). Missing data for BCVA will be imputed using the last observation carried forward (LOCF). The formal non-inferiority test will be performed at Week 52 with a non-inferiority margin of 10% at an alpha level of 0.049. This alpha reflects an adjustment of 0.001 for the unmasked data review by the data safety monitoring committee (DSMC) for safety assessments. The total alpha spent of 0.001 for the DSMC is based on the assumption of no more than 10 unmasked reviews during the study, with 0.0001 allocated to each review. Thus, the overall alpha for the study is preserved at 0.05 level.

For hypothesis testing, if the lower limit of the 95.1% confidence interval for the difference between an abicipar group and ranibizumab is greater than or equal to -10%, non-inferiority of the abicipar group is established.

Multiplicity for the primary efficacy analysis will be controlled using a gatekeeping procedure defined by the following sequence to control the overall type I error rate at 0.05 level:

- **Step 1:** Testing for non-inferiority of abicipar 2Q8 against ranibizumab
- **Step 2:** Testing for non-inferiority of abicipar 2Q12 against ranibizumab

Hypothesis testing for abicipar 2Q12 against ranibizumab is valid only if non-inferiority for abicipar 2Q8 against ranibizumab is established.

If both abicipar groups have demonstrated non-inferiority to ranibizumab using the PP population, hypothesis testing for superiority will be performed using the ITT population for each abicipar group following the same order as defined above for non-inferiority testing. Superiority of abicipar will be demonstrated if the lower confidence limit for the treatment difference is greater than zero.

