Tipping point analysis as described in Section 5.2.4.2 will be performed for BCVA change using the PP population. The tipping region will be constructed based on the combinations of values for δ_{2Q8} , δ_{2Q12} , or δ_{rQ4} that resulted in a lower bound of the 95.1% CI for the difference of abicipar (2Q8 or 2Q12) minus ranibizumab less than -5 letters.

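### Does SAP Appendix A use the wrong divisor in its stratified confidence interval, and does that interval contradict the method cited in SAP 5.2.2?

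*SAP*

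**What the plan says.** SAP 5.2.2 describes the primary stable-vision comparison: "the confidence intervals for treatment group differences will be calculated using the CMH weighted method with the baseline BCVA" group (≤ 55 versus > 55 letters) as the stratification factor, with a 2010 paper cited for the description. On missing values it says "Missing data for BCVA will be imputed using the last observation carried forward (LOCF"). Non-inferiority is declared if the lower limit of the 95.1% interval is at or above -10%. SAP section 12 gives the title of the cited paper: "Stratified Wilson and Newcombe confidence intervals for multiple binomial proportions".

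SAP Appendix A is headed "Appendix A: Modified Wald Confidence Interval with Stratifications". Its first half, for LOCF data, defines for each arm and stratum the raw proportion p = x/n and a shrunken proportion p* = (x+2)/(n+4). The stratum difference d_i uses the raw proportions. The variance in each arm is p*(1-p*)/n. Strata are combined with weights w_i = n1·n2/(n1+n2), and the interval is d ± z·sqrt(v(d)).

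Its second half, for multiple imputation, lets a symbol "denote the variance V(d) for the point estimate from the" j-th imputed data set, and enters the square root of V(d) "as the STDERR for PROC MIANALYZE". Both halves therefore share one variance.

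**The concern.** Two things catch the eye. First, p* has n+4 in its denominator while its variance has n. A reader who knows the add-two-successes, add-two-failures interval expects n+4 in both places. On that reading every stratum variance is too large by the factor (n+4)/n, and the excess passes to the LOCF interval, the multiple-imputation interval and, through SAP 5.3.3, the 15-letter-gain comparison.

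Second, SAP 5.2.2 cites a paper whose title names Wilson and Newcombe intervals, while the appendix writes out a modified Wald interval under an LOCF heading that matches 5.2.2. If both were meant as the primary interval, one decision rule would have two formulas. At stake would be a little power and a primary limit that is not uniquely defined. Inflated type I error was never the issue, because the divisor n makes the interval wider.

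**Working it through.** **Inputs.** From SAP 1.2: 240 per arm, 90% response in both arms, margin 10%. From SAP 5.2.2: alpha 0.049, so z = 1.9686, and two BCVA strata. The stratum sizes are not given, so 120/120, 96/144 and 72/168 per arm are assumed.

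**The plan's own figure.** The unpooled normal approximation gives SE = sqrt(2 × 0.09/240) = 0.02739 and 0.10/0.02739 = 3.651. Power is Phi(3.651 - 1.960) = 95.5% at alpha 0.05 and Phi(3.651 - 1.969) = 95.4% at alpha 0.049. The stated power of approximately 95% is reproduced.

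**Size of the divisor effect.** Take strata 120/120 with 108 of 120 stable in every cell.
- p* = 110/124 = 0.8871, and p*(1-p*) = 0.10016.
- Divisor n: each cell has variance 0.10016/120 = 0.0008346. With two arms and two equal strata, v(d) = 2 × 0.0008346/2 = 0.0008346. The half-width is 1.9686 × 0.02889 = 5.69 points.
- Divisor n+4: v(d) = 0.10016/124 = 0.0008077, and the half-width is 5.59 points.
- Ratio: sqrt(124/120) = 1.0165. The other two splits give 1.0166 and 1.0167.
- Plain Wald: the half-width is 5.39 points. Of the 0.30-point widening over plain Wald, 0.09 comes from the divisor and the rest from p*.

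So the 1.7% is correct arithmetic. The question is whether n+4 is the right yardstick.

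**Which divisor fits the estimator.** The point estimate is a weighted sum of x1/n1 - x2/n2, with no shrinkage. The binomial variance of x/n is p(1-p)/n. The only unknown is p, and p* is used to estimate it, which keeps the variance from collapsing when the raw proportion is near 1. The result is p*(1-p*)/n. A divisor of n+4 belongs with an interval centred on p*, and the appendix does not centre there. Changing only the divisor would leave an unadjusted centre with a variance built for an adjusted one. The same holds for the multiple-imputation half, where the estimate is again the unadjusted weighted difference. Nothing in the documents states n+4 as the intended divisor.

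**How the two versions perform.** The four stratum-by-arm counts were enumerated exactly, with the rule that the lower limit is at least -10%. Response rates are abicipar versus ranibizumab. One-sided type I error at the margin (nominal 2.45%):

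| Assumed setting | Divisor n | Divisor n+4 |
|---|---|---|
| 80% vs 90%, 240 per arm, strata 120/120 | 2.26% | 2.45% |
| 85% vs 95%, 240 per arm, strata 96/144 | 2.16% | 2.32% |
| 75% vs 85%, 240 per arm, strata 96/144 | 2.33% | 2.50% |
| 80% vs 90%, 300 per arm, strata 120/180 | 2.30% | 2.46% |
| 80% vs 90%, abicipar 220, ranibizumab 260, 40/60 strata | 2.36% | 2.59% |
| 80% vs 90%, abicipar 200, ranibizumab 260, 40/60 strata | 2.40% | 2.63% |
| 80% vs 90%, abicipar 260, ranibizumab 200, 40/60 strata | 2.08% | 2.24% |

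Power at 90% in both arms (240 per arm, strata 96/144) is 94.1% with n and 94.5% with n+4. The two verdicts differ in 0.44% of trials there, and in 0.12% at 300 per arm. Unequal arms are plausible, since the per-protocol rules in SAP 2.1 need not remove the same number from each group.

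**The citation.** The sentence in SAP 5.2.2 cites the paper for the CMH-weighted, stratified method. Appendix A uses CMH-type weights, n1·n2/(n1+n2), so the two places agree on the weighting. Only the title of the paper is available, and a title does not show which intervals the paper covers or which part the SAP relies on. The appendix's role may also be set out in text that is not visible. SAP 5.3.1 says "Tipping point analysis as described in Section 5.2.4.2 will be performed for BCVA change using the PP population", yet the visible SAP passes from 5.2.2 straight to 5.3. A gap of that kind cannot be counted as an omission from the plan.

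**The case for a change.** The best case for the concern is that performance supports n+4. At 80% versus 90%, two-sided coverage as written is 95.65% against a nominal 95.1%, while n+4 gives about 95.3% and a one-sided error almost exactly at nominal. The divisor can also decide a trial. With strata 96/144, abicipar 80 and 124 stable and ranibizumab 84 and 129 stable, the lower limit is -10.03 with n and -9.93 with n+4. Finally, a programmer could read SAP 5.2.2 as a Newcombe interval or follow Appendix A, and a confirmatory rule should point to one formula.

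The figures stand, and the interval as written is slightly conservative. That does not make it wrong. The close agreement with nominal at 80% versus 90% belongs to that setting, and the table shows n+4 passing 2.45% in others. The borderline counts were found by a grid search, so they show that a reversal is possible and say nothing about how often it occurs.

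On the citation, two codings of a stratified Newcombe interval give lower limits of -5.50 and -5.59, against -5.69 for the appendix. They disagree with it in 0.3 to 0.65% of trials at 90/90, and the appendix is nearly always the stricter. Those codings are assumptions about a method that the documents do not spell out. What remains is that the visible 5.2.2 does not name Appendix A. A cross-reference would be tidy, but its absence from the visible text is not a flaw in the analysis.

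**Conclusion.** The concern does not hold. Dividing by n is a coherent plug-in variance for the unadjusted difference on which the interval is centred, so there is no error to correct. The 1.7% is a comparison with a different formula. Moving to n+4 would gain about 0.4 points of power (94.1% to 94.5% at 90% in both arms, 240 per arm). In exchange, the one-sided error would exceed 2.45% in some plausible settings, where the formula as written stayed below it in every setting checked. For a pivotal non-inferiority test the slightly stricter interval is a defensible choice. The alleged conflict with SAP 5.2.2 is not shown: the weighting agrees, only the paper's title is available, and sections that could state the appendix's role are not visible. Either interval would support a sound conclusion.

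The figures rest on assumed stratum splits, response rates and arm sizes, and on the same rates in both strata. The argument about the divisor rests on none of these.
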